9.3 POPULATIONS FOR ANALYSES

All participants who complete the baseline interview will be included in the analyses in accordance with intention to treat (ITT) analysis.

9.4 STATISTICAL ANALYSES

9.4.1 GENERAL APPROACH

Descriptive analyses of the study sample will include percentages for categorical variables and means and standard deviations for continuous measures. Chi-square tests and t-tests will be computed to compare study arms on baseline sociodemographic measures. We will compare follow-up between conditions using GEE logistic regression. Results will be reported as odds ratios with 95% confidence intervals and exact p-values for 2-tailed tests.

We will examine the distributions of outcome measures to ascertain whether there is sufficient variability to analyze frequency measures as ordinal. Response categories with a small number of responses will be collapsed for analysis. We will analyze missing data patterns to assess the extent of missing data, and to determine if there is evidence of non-ignorable missingness (i.e. missing not at random, MNAR).

We will conduct repeated measures linear, logistic, and modified Poisson regressions using mixed effects models with random intercepts for subject and recruitment site to test the effect of intervention condition on changes in mediator and outcome variables. In the event of missing data in more than 5% of cases, or unbalanced loss-to-follow-up, analyses will be conducted in Mplus using full-information maximum likelihood methods. We will include the interaction of time and participant type (intervention participant vs. network member) to test for differential effects. Following analysis of the main outcomes we will conduct analyses to explore hypothesized mediation and moderation effects.

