9.2 SAMPLE SIZE DETERMINATION

We estimated power allowing up to 10% attrition among intervention participants and up to 15% attrition among network members. Power calculations were computed using PASS software and considering effects observed in the pilot study.

We expect to see large reductions in syringe sharing and condomless sex in the MASLIHAT intervention group, and little change in these behaviors in the control group. In the pilot study, syringe sharing decreased from 52% at baseline to 0% at six months, and condomless sex decreased from 35% at baseline to 1% at six months. For binary outcomes, we computed Mixed Models Tests for Two Proportions in a 3-Level Hierarchical Design (Level-3 Randomization), with an intracluster correlation of 0.05 and alpha=.01. We computed power for outcomes ranging from 0.30 to 0.50 for the control group, and 0.05 to 0.15 for the MASLIHAT intervention group, and with 10, 20 or 30 subjects per cluster, representing intervention participants, network members, and the complete sample. We will have at least 80% power to detect predicted changes in condomless sex, and over 90% power to detect predicted changes in syringe sharing. In the larger sample, we will have adequate power to detect effects even if they are not as large as anticipated.

The intervention also targets alcohol use and in the pilot study, days of alcohol use in the past month decreased from 5 to 2, with $b/SE = -6.52$, yielding a Cohen's d effect size of -0.69. We estimated power by computing Mixed Models Tests for the Slope Difference in a 3-Level Hierarchical Design with Fixed Slopes (Level-3 Randomization), with subject $icc=0.30$ and $alpha=0.01$, for a standardized mean difference (SMD) of 0.50 to 0.70, with cluster sizes of 10, 20. and 30. For the intervention participants, we will have at least 80% power to detect a $SMD=0.70$; for network members we will have at least 80% power to detect a $SMD=0.50$, and for the complete sample we will have at least 80% power to detect a $SMD=0.41$.

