9.4.2 ANALYSIS OF THE PRIMARY ENDPOINT(S)

Relative frequency of syringe sharing, equipment sharing, and vaginal or anal sex without a condom in the past 3 months will be measured at each time point on a 7-point Likert-type scale (Never, Rarely, Less than half the time, About half the time, More than half the time, Most of the time, Always). We will analyze ordinal outcomes, and we will also dichotomize responses to analyze binary (none/any) outcomes.

We will conduct repeated measures mixed effects regressions with random intercepts for subject and recruitment site to test the effect of intervention condition on changes in the outcome variables. We will use ordinal logistic regression for ordinal outcomes and modified Poisson regression for binary outcomes. We will conduct a test of the proportional odds assumption with a likelihood ratio test comparing the proportional odds model with a non-proportional odds model.⁷⁴ We will include the interaction of time and participant type (intervention participant vs. network member) to test for differential effects. If the interaction term suggests differential effects ($p < .10$), we will stratify analyses by participant type. Sociodemographic characteristics (age, education, time in Moscow) will be included as covariates in the analysis if they are related to the outcome at baseline or if they vary significantly across conditions. All participants with at least one follow-up interview will be included in the analysis.

Dosage: If there is variability in attendance, we will estimate repeated measures mixed effect models predicting outcomes with session attendance and the interaction between time, intervention condition, and session attendance as predictors. A significant interaction effect will indicate that the effect of the intervention is moderated by session attendance.

Social Network Diffusion. Additional analyses among network members will examine associations between exposure to intervention concepts (i.e. conversations about health, drugs/alcohol HIV) and changes in outcomes over time.

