The results of mixed effects ordinal logit models will be reported as odds ratios with 95% confidence intervals, and exact p-values. Predicted probabilities will be computed from the logit model. The results of mixed effects modified Poisson regressions will be reported as relative risk ratios with 95% confidence intervals, and exact p-values. We will also report intra-class correlations for the subject and site (cluster) levels.

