9.4.3 ANALYSIS OF THE SECONDARY ENDPOINT(S)

Secondary outcomes are HIV and HCV incidence over 12 months. Participants who are HIV antibody positive at baseline will be excluded from the analysis. Participants who are HCV RNA positive at baseline and at 6-months (i.e. chronic infection) will be excluded from the analysis. HCV infection will be operationalized as a positive antibody test following a negative antibody test, or for persons who are AB+ at baseline, a positive HCV RNA test following a negative HCV RNA test. We will conduct a missing data analysis to check for differences between participants with and without test results. If more than 5% of the data are missing we will employ full-information maximum likelihood methods using Mplus.

We will compare incidence rates of HIV and HCV infection between the two intervention conditions among intervention participants, and among network members, with GEE modified Poisson regression to estimate relative risks, adjusted for clustering by recruitment site.⁷⁵ We will estimate the effect of intervention condition, adjusting for covariates including age, education, duration of injection, and length of time in Russia if they are related to the outcome at baseline or if they vary significantly across conditions. The results will be reported as relative risk ratios with 95% confidence intervals, and exact p-values.

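### Binary primary outcomes are assigned a random-intercept Poisson model that does not fit 0/1 data; with no variance estimator named, neither usual choice of standard error is right with 12 sites

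*Combined protocol and SAP*

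**What the plan says.** Section 9.4.1 plans repeated-measures "modified Poisson regressions using mixed effects models with random intercepts for subject and recruitment site". Section 9.4.2 splits the primary outcomes by form: "We will use ordinal logistic regression for ordinal outcomes and modified Poisson regression for binary outcomes". It then states: "The results of mixed effects modified Poisson regressions will be reported as relative risk ratios with 95% confidence intervals, and exact p-values". It adds: "We will also report intra-class correlations for the subject and site (cluster) levels", without saying which model supplies them.

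For HIV and HCV incidence, Section 9.4.3 takes a different route, "with GEE modified Poisson regression to estimate relative risks, adjusted for clustering by recruitment site". Neither 9.4.1 nor 9.4.2 says whether the intervals from the mixed Poisson model are model-based or robust, or at what level a robust variance would be clustered. No section mentions a correction for the small number of sites.

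**The concern.** Modified Poisson regression works for binary data because it is an estimating-equation method. The Poisson variance, p, is wrong for a 0/1 response, whose variance is p(1−p), and a sandwich estimator replaces it. Inside a random-effects likelihood the wrong variance does more than set the standard errors: it also determines the variance components. Binary data look under-dispersed relative to Poisson, so real between-subject variation is absorbed and the subject variance is pushed down.

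Two things are at stake. The first is the confidence intervals and p-values for the dichotomised syringe-sharing, equipment-sharing and condomless-sex outcomes. The second is the subject ICC, which later trials may use for planning.

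**Working it through.** **Inputs.** There are 12 sites, 6 per arm (6.3), with 10, 20 or 30 men per site, "with an intracluster correlation of 0.05 and alpha=.01", and "outcomes ranging from 0.30 to 0.50 for the control group, and 0.05 to 0.15 for the MASLIHAT intervention group" (all 9.2). Pilot baselines were 52% for syringe sharing and 35% for condomless sex (9.2). There are five interviews per man (8.1) and "exact p-values for 2-tailed tests" (9.4.1). The only subject ICC given is 0.30, for the alcohol outcome (9.2). None is given for the binary outcomes, so 0.15, 0.30 and 0.45 are assumed.

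**1. The plan's own power.** With 10 men per site there are 60 per arm. The design effect is 1 + 9 × 0.05 = 1.45, so the effective n is 60/1.45 = 41.4.
- 0.35 v 0.05: SE = √[(0.2275 + 0.0475)/41.4] = 0.0815. Then 0.30/0.0815 − 2.576 = 1.10, and power is 86.5%.
- 0.50 v 0.10: SE = √[(0.25 + 0.09)/41.4] = 0.0906. Then 0.40/0.0906 − 2.576 = 1.84, and power is 96.7%.

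The stated figures (at least 80% and over 90%) reproduce. They come from a two-proportion calculation that says nothing about the Poisson model's behaviour.

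**2. Model SE of the change contrast, no effect.** With balanced data and visit as a factor, the Poisson mixed model gives the arm-by-12-month log relative risk a variance of Σ over arms of [1/(n p₀) + 1/(n p₁₂)], whatever the intercept variance. At 180 men per arm and p = 0.52 the SE is √[4/(180 × 0.52)] = 0.207. For 0/1 data with within-subject correlation ρ, each arm's true variance is 2(1−p)(1−ρ)/(n p). The ratio of model SE to true SE is therefore 1/√[(1−p)(1−ρ)]:
- ρ = 0.15: 1.35 at p = 0.35 and 1.57 at p = 0.52.
- ρ = 0.30: 1.48 and 1.73.

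**3. When the subject variance goes to zero.** A man's total over m visits has variance m p(1−p)[1 + (m−1)ρ]. The Poisson fit sees extra variation only if this exceeds m p, that is, if ρ > p/[(1−p)(m−1)]. With m = 5 and site variation ignored, the thresholds are 0.35/(0.65 × 4) = 0.135 and 0.52/(0.48 × 4) = 0.271.

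**4. Simulation with site variation.** Binary data came from a logistic-normal model with site ICC 0.05: 12 sites × 30 men × 5 visits. They were fitted by maximum likelihood to the Poisson model with both intercepts, with time coded as baseline v follow-up (150 runs per setting, Monte Carlo error about 6% on each ratio).

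| Quantity | Result |
|---|---|
| Fitted subject SD below 0.1, ρ = 0.15 | 89–100% of fits |
| Same, ρ = 0.30 | 1–3% (35% baseline); 71–83% (52% baseline) |
| Same, ρ = 0.45 | 0–6% |
| Model SE / empirical SD, condition-by-time, no effect | 1.22–1.77 |
| Same, 35%→10% or 52%→10% | 0.97–1.13 |
| Model SE / empirical SD, between-arm at follow-up | 0.70–0.89 in all 12 settings |
| Site sandwich SE / empirical SD, condition-by-time | 0.81–0.90 |
| Null rejection at nominal 5%, condition-by-time | 0–1.3% model-based; 9–11% sandwich |

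**5. The 12-month contrast itself** (6 × 30 men per arm, 4,000 runs). The ratios below are at a correlation of about 0.28, with the range over 0.17–0.41 in brackets.
- No effect: 1.46 (1.34–1.58) at 35%; 1.72 (1.56–1.88) at 52%.
- 50%→15%: 1.20 (1.19–1.26).
- 35%→10%: 1.16 (1.11–1.23).
- 52%→10%: 1.13 (1.09–1.13).
- 35%→5%: 1.01 in a separate run at within-subject ICC 0.24.

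For this contrast under no effect, an uncorrected site sandwich was 10–15% too narrow, with 10–12% rejection. A small-sample correction with t on 12 − 2 = 10 df brought rejection to about 4–6%.

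**The case against.** The strongest reply is that the word modified already implies a sandwich, so nothing in the text commits the trial to model-based standard errors. That is correct. A reader might infer that the reported intervals will be far too wide; the documents do not support this, because they leave the estimator unstated. Section 9.1 also promises a formal SAP, which could supply it. Naming a plain sandwich there would not be enough, however: with 12 sites it over-rejects, and it leaves the variance components as they were.

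Three further limits stand.
- Large inflation belongs to the no-effect case. Under planned-size effects it is modest, and rejection in a full-sample check stayed at or above 99.5% at the 5% level even with model-based errors.
- Collapse of the subject variance is not general. At a 35% baseline and correlation 0.30 it was rare.
- Section 9.4.2 does not say that the ICCs come from the Poisson model. The harm to the ICC arises only if they do.

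**Conclusion.** The concern holds in a bounded form. The model named for the binary outcomes has a misspecified likelihood, and neither natural reading of its variance gives correct error rates. For the 12-month change contrast, model-based errors are about 35–65% too wide under no effect, and more at high prevalence with higher correlation. Under planned-size effects they are about 5–25% too wide, with almost no excess in some settings. An uncorrected site sandwich errs the other way.

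It would be wrong to conclude that the fault is simply conservative. The between-arm contrast at follow-up had model-based errors 11–30% too small. The check did not separate misspecification from the small number of sites as the cause.

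The sizes depend on assumed within-subject correlations, complete data and a logistic-normal generating model, and pair matching was ignored. Only the dichotomised analyses are affected; the ordinal-logit analyses of the same behaviours are not.

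**What to change.** In 9.4.1 and 9.4.2, replace the model for binary outcomes with one of the following:
- GEE modified Poisson clustered by recruitment site, with a small-sample-corrected sandwich and a t reference on about 10 df; or
- a mixed logistic model, with risks standardised to relative risk and risk difference.

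Add the same small-sample correction to 9.4.3, which has the GEE but not the correction. State that ICCs for binary outcomes come from the logistic model or from ANOVA on the 0/1 responses.

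The change is to wording only, but it has two costs. GEE needs missing data handled separately, by weighting or imputation, because the full-information likelihood fallback in 9.4.1 would not apply. An honest reference distribution also lowers nominal power: the 86.5% for 0.35 v 0.05 with 10 men per site becomes about 69% with t on 10 df at alpha 0.01.

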9.4.2 ANALYSIS OF THE PRIMARY ENDPOINT(S)

Relative frequency of syringe sharing, equipment sharing, and vaginal or anal sex without a condom in the past 3 months will be measured at each time point on a 7-point Likert-type scale (Never, Rarely, Less than half the time, About half the time, More than half the time, Most of the time, Always). We will analyze ordinal outcomes, and we will also dichotomize responses to analyze binary (none/any) outcomes.

We will conduct repeated measures mixed effects regressions with random intercepts for subject and recruitment site to test the effect of intervention condition on changes in the outcome variables. We will use ordinal logistic regression for ordinal outcomes and modified Poisson regression for binary outcomes. We will conduct a test of the proportional odds assumption with a likelihood ratio test comparing the proportional odds model with a non-proportional odds model.⁷⁴ We will include the interaction of time and participant type (intervention participant vs. network member) to test for differential effects. If the interaction term suggests differential effects ($p < .10$), we will stratify analyses by participant type. Sociodemographic characteristics (age, education, time in Moscow) will be included as covariates in the analysis if they are related to the outcome at baseline or if they vary significantly across conditions. All participants with at least one follow-up interview will be included in the analysis.

Dosage: If there is variability in attendance, we will estimate repeated measures mixed effect models predicting outcomes with session attendance and the interaction between time, intervention condition, and session attendance as predictors. A significant interaction effect will indicate that the effect of the intervention is moderated by session attendance.

Social Network Diffusion. Additional analyses among network members will examine associations between exposure to intervention concepts (i.e. conversations about health, drugs/alcohol HIV) and changes in outcomes over time.

The results of mixed effects ordinal logit models will be reported as odds ratios with 95% confidence intervals, and exact p-values. Predicted probabilities will be computed from the logit model. The results of mixed effects modified Poisson regressions will be reported as relative risk ratios with 95% confidence intervals, and exact p-values. We will also report intra-class correlations for the subject and site (cluster) levels.

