Peer educator personal development. Measures of peer educator personal development (in addition to knowledge and behavior change) will be administered at baseline and at 12-month follow-up, including self-esteem, self-efficacy, and substance use self-stigma. The 10 items of the Rosenberg Self-Esteem Scale^{70, 71} assess a person's overall evaluation of his or her worthiness as a human being, including subscales of self-competence and self-liking. Items are rated on a 4-point scale from 1 (strongly disagree) to 4 (strongly agree). The New General Self-Efficacy Scale⁷² includes 8 items to measure general self-efficacy (e.g. "I will be able to achieve most of the goals that I set for myself.") rated on a Likert scale from strongly disagree to strongly agree. Internalized stigma of substance use will be assessed with 6 items adapted from a measure of HIV stigma⁷³, rated on a 5-point Likert-type scale, e.g. "I feel ashamed of being a person who uses drugs".

Intervention engagement

Session facilitators will record participant attendance, note homework completion, and rate participant engagement at each session.

HIV/HCV counseling and testing.

Intervention participants and network members will be referred to the Moscow HIV Prevention Center (MHPC) for voluntary HIV/HCV rapid and confirmatory testing and counseling following the baseline interview, and later at the 6-month (HCV) and 12-month (HIV and HCV) follow-up. We chose to not require HIV testing as a condition of study enrollment as its impact on study recruitment and participation are unknown. Participants will be informed that their results will be shared with the research study unless they choose to opt out. We will explain the measures we will employ to maintain the confidentiality of the results.

We will give each participant a card with a code number on which test results will be reported. The testing code number will be separate from the research ID number used to identify interviews, and will

consist of a group number and an individual code. The list matching testing codes with research IDs will be kept in a secure REDCap database separate from locator data and interview data. Participants who object to having their test results linked to their personal interview data will be given the option of blacking out the individual code number, keeping only the group number. This will allow us to track results by intervention group even if the results cannot be linked to individuals.

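### Only 12 sites are randomised and section 9.4 names no small-cluster method, so the HIV/HCV test runs at about 7.5 to 10.5% instead of 5% unless site matching is effective

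*Combined protocol and SAP*

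**What the plan says.** Sections 5.5 and 6.3 pair-match 12 recruitment sites and randomise one of each pair to MASLIHAT, so each arm has six independent units.

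For the primary outcomes, 9.4.2 specifies "repeated measures mixed effects regressions with random intercepts for subject and recruitment site to test the effect of intervention condition on changes", and adds: "We will use ordinal logistic regression for ordinal outcomes and modified Poisson regression for binary outcomes". For infection, 9.4.3 compares incidence "among intervention participants, and among network members, with GEE modified Poisson regression to estimate relative risks, adjusted for clustering by recruitment site".

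Both 9.4.1 and 9.4.3 contain a missing-data switch: "In the event of missing data in more than 5% of cases, or unbalanced loss-to-follow-up, analyses will be conducted in Mplus" and "If more than 5% of the data are missing we will employ full-information maximum likelihood methods using Mplus".

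None of 9.4.1 to 9.4.3 names a df method, a small-sample sandwich correction, a cluster-level or permutation test, a site-by-time effect or a pair term. The p-values are called exact, but no exact test is described, so this reads as a reporting format. Section 9.1 promises a formal SAP before the first interim analysis; no such text is in the documents supplied.

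On power, 9.2 states: "We will have at least 80% power to detect predicted changes in condomless sex", using an ICC of 0.05 and alpha 0.01.

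**The concern.** The precision of a comparison of six sites with six rests on about 10 df, however many men are interviewed. A site-clustered sandwich estimated from 12 clusters is biased downward, and a normal reference ignores the uncertainty in that estimate. Both errors make intervals too narrow and reject a true null too often.

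The HIV and HCV comparisons are the most exposed, because 9.4.3 commits to this kind of estimator and analyses index participants and network members separately. A nominally significant reduction in incidence could then carry about twice the stated false-positive risk. The index-participant stratum is also exposed, through a power statement that appears to use a normal reference.

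**Working it through.** **Inputs from the documents.** 12 sites in 6 pairs (5.5, 6.3). From 9.2: ICC 0.05 and alpha 0.01 for binary outcomes; 10, 20 or 30 men per site; HIV base rate 10% with 30 per site; HCV 40% with 15 per site; between-site CV 0.5 (control) and 1 (intervention); pilot condomless sex 35% falling to 1%. The 5% test level is inferred from the 95% intervals and two-tailed tests in 9.4.

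**Assumed.** Uncorrected sandwich with a normal reference, since nothing else is named; the share of site variance removed by matching; autocorrelation of site effects over time.

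**1. Reproducing the stated power.** Effective number per arm = 6m / (1 + (m − 1) × 0.05). For m = 10 this is 60 / 1.45 = 41.4. For 35% v 5%:

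- pooled SE = √(2 × 0.20 × 0.80 / 41.4) = 0.0879, and 0.30 / 0.0879 = 3.41;
- unpooled SE = √((0.2275 + 0.0475) / 41.4) = 0.0815, and 0.30 / 0.0815 = 3.68.

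Against 2.576 these give 80% and 87%, so the stated figure reproduces. Referring the same ratios to other distributions (noncentral t, one time point):

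| Setting | Normal | 10 df | 5 df, matching removes nothing |
|---|---|---|---|
| Index, 35% v 5%, alpha 0.01 | 80–87% | 61–69% | 41–47% |
| Index, 35% v 5%, alpha 0.05 | 93–96% | 87–91% | 78–83% |
| Index, 35% v 1% (pilot), alpha 0.01 | 93–97% | 78–87% | 56–67% |
| Full sample (m = 30), 35% v 5%, alpha 0.01 | 98–99% | 88–93% | 68–75% |

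**2. HIV/HCV sizing.** Clusters per arm = 1 + (1.645 + 0.842)² × [(λ0 + λ1)/m + 0.5²λ0² + 1²λ1²] / (λ0 − λ1)².

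- HIV (λ1 = 0.011): 1 + 6.18 × 0.00632 / 0.00792 = 5.93.
- HCV (λ1 = 0.086): 1 + 6.18 × 0.0798 / 0.0986 = 6.00.

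Six per arm fits only with the added 1; without it, power would be about 86%. The sizing thus appears to allow for few clusters, while the analysis in 9.4.3 does not.

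**3. Type I error in closed form.** For six v six site means with no pair effect, the uncorrected sandwich divides by 6 where 5 is needed, so variance is understated by 5/6. The actual level is P(|t10| > 1.96 × √(5/6)) = P(|t10| > 1.789) = 10.4%. An unbiased variance with a normal reference gives 7.8%.

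**4. Type I error for the stated HIV/HCV model by simulation** (6 pairs; 20,000 null trials per setting; 10 to 30 men per site for HIV, 5 to 15 for HCV; site CV 0 or 0.5):

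| Method | Matching removes nothing | Matching removes 50–75% (assumed; CV 0.5) |
|---|---|---|
| Uncorrected sandwich, normal | about 7.5–10.5% | HIV about 5.5–8%; HCV about 2.5–5.5% |
| Kauermann-Carroll sandwich, t(10) | 2.2–4.9% | 0.8–3.1% |
| Site-level t(10) | 4.3–5.3% | 0.9–3.5% |
| Paired site-level t(5) | 4.3–5.6% | 4.3–5.6% |

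A separate set with site ICC 0.005 or 0.05 instead of a fixed CV gave 7.6 to 11.1% for the uncorrected test with no pair effect at these two base rates.

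**5. Missing-data route.** Modelled, by assumption, as a site random-intercept logit by maximum likelihood with a normal reference, HIV/HCV error is 2.2 to 7.7% without a pair effect and 1.9 to 4.5% with one. The amount of missing data would therefore change the behaviour of the test.

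**6. Primary outcomes, no pair effect unless stated.**

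- Arm-by-time, modified Poisson with a site-clustered sandwich: 9.8–10.2%.
- Arm-by-time, ordinal with random intercepts: 5.1–5.2% if site effects are constant; 5.9–17.5% at assumed autocorrelation 0.9 to 0.5 (850 trials per setting).
- Mixed Poisson without a sandwich: 0.4–4.4%.
- 12-month value adjusted for baseline, normal reference: 6.2–9.5%; 3.2–5.9% with pairs; 3.5–6.1% with t(10) and no pair effect.

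**The case against.** A formal SAP is promised and is a usual place for these choices. That is fair, and it is also when the fix is cheapest, but nothing supplied shows what it will contain.

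Three stronger readings are tempting, and the documents do not support them.

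- A reader might infer that ignoring the pairs inflates error. Mostly the reverse holds: when matching works and is ignored, error usually falls and unpaired t-tests become conservative. An unpaired analysis of a matched design is defensible.
- A reader might infer that the primary analyses are shown to be anti-conservative. The plan does not state the contrast, the sandwich level or whether site effects change over time. Depending on these, error is below, at or above nominal, and the largest figures rest on an assumed autocorrelation.
- A reader might infer that 80% power is reachable only with a normal reference. That holds for 35% v 5% at alpha 0.01, but the pilot's 35% v 1% gives 78–87% with 10 df.

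Nor is the missing-data switch certain for behaviour. The plan says "We estimated power allowing up to 10% attrition among intervention participants and up to 15% attrition among network members", which sets ceilings, and the pilot in 2.2 lost 3 of 90 men (3.3%) over six months, below the 5% trigger. For infection the switch is more plausible, because testing is voluntary: "We chose to not require HIV testing as a condition of study enrollment".

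Finally, if effects are as large as in the pilot, the full-sample behavioural result should survive any of these choices.

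**Conclusion.** The omission is certain. For HIV/HCV, a standard run of the stated analysis has Type I error of about 7.5 to 10.5% at nominal 5%, with intervals correspondingly too narrow, if matching removes no site variance. If matching removes half to three quarters, HIV error is still about 5.5 to 8%, while HCV is about 2.5 to 5.5%. The documents do not say how effective the matching is. This rests on an uncorrected sandwich and a normal reference being used, which the plan neither states nor excludes.

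For the primary outcomes inflation is possible but not shown. Index-participant power for 35% v 5% at alpha 0.01 is overstated if site-level df are used (61–69%); full-sample power is adequate (88–93%).

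The df also depend on an unresolved count. Sections 5.5 and 6.3 give 12 sites, yet 5.5 also gives two groups per site and 20 groups in total, which implies 10. Four groups per quarter over 18 months, in the same paragraph, is 4 × 6 = 24 groups, which fits 12. With 10 sites the closed-form error rises to about 11.8%. The point should be fixed, and it does not invalidate the design.

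**What to change.** In 9.4 or the formal SAP, before outcome data are seen:

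- **9.4.3:** use a bias-corrected site sandwich (for example Kauermann-Carroll) with t on sites minus 2 df, or a site-level t-test. Keep the same site-level reference if the Mplus route is used.
- **9.4.2:** state the tested contrast and use site-level df for the condition effect. If arm-by-time is tested, add a random site-by-time effect or use a t-test on site-level changes. For modified Poisson, specify a bias-corrected sandwich at site level.
- **Pairing:** state in advance whether the analysis is paired (pairs minus 1 df), which held its level in the settings tried. Unpaired is near nominal or conservative for HIV/HCV, and up to about 6% for the baseline-adjusted primary model with t(10). Do not rely on a within-pair permutation test at 0.01: six pairs give 64 allocations and a smallest two-sided p of 2/64 = 0.031.
- **9.2:** restate index-participant power on the chosen df and on the alpha the analysis will use.
- **Site count:** reconcile 12 sites with 20 groups first. The df are 10 and 5 for 12 sites, 8 and 4 for 10.

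Cost: wording only. Intervals widen relative to the uncorrected sandwich by about 25% (1.095 × 2.228 / 1.960 = 1.245) with 10 df, or about 44% (1.095 × 2.571 / 1.960 = 1.436) with 5 df if matching removes nothing. In that last case pairing also costs 8–9 points of index power at alpha 0.05 and 20–22 points at 0.01, compared with 10 df.
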